5.3.2 Lirilumab and 5-azacytidine dose adjustments for non-hematologic drug-related AEs

Investigators should, whenever possible, determine which medication is causing the toxicity and interrupt or dose reduce 5-azacytidine and/or interrupt lirilumab, as applicable. No dose reductions (only interruptions) are permitted for lirilumab. Dose reductions of azacytidine will be as per Table 1. Thus, if dose level 0 is established as the MTD, one and two dose level reductions of azacytidine will be azacytidine 50 mg/m² x 7 days and azacytidine 25 mg/m² x 7 days, respectively. If the MTD is below dose level 0 further dose reduction levels of 5-azacytidine will be defined before moving to the phase II portion of the study.

Table 2 Dose adjustments for non-hematologic drug-related adverse events, clinically significant in the opinion of the investigator

Grade	Occurrence	Dose modification
1 or 2	Any time	No dose reduction.
3 or 4 (Persistent grade 2: Consider similar dose adjustments if persistent and not responding to optimal management in the opinion of PI and treating physician)	1st and 2nd time	Hold lirilumab and 5-azacytidine. Resume lirilumab and 5-azacytidine at prior dose if recovery to ≤ Grade 1 occurs within 14 days. If toxicity persists for 15-28 days, hold therapy and resume at ONE dose level below current dose for 5-azacytidine and prior dose of lirilumab ONLY after recovery to ≤ Grade 2. Dose re-escalation to prior dose of 5-azacytidine is permitted in accordance with the dose-escalation guidelines in section 5.3.6.
	3 rd and 4th time	Hold lirilumab and 5-azacytidine. Follow until toxicity ≤ Grade 2. Resume lirilumab at prior dose and 5-azacytidine at ONE dose level below current dose. Dose re-escalation of 5-azacytidine to prior dose is permitted in accordance with the dose-escalation guidelines in section 5.3.6.
	5th time	Hold lirilumab and 5-azacytidine. Follow until toxicity ≤ Grade 2. Resume lirilumab at prior dose and 5-azacytidine at TWO dose levels below current dose. Dose re-escalation of 5-azacytidine by ONE dose level every 4 weeks is permitted in accordance with the dose-escalation guidelines in section 5.3.6.

5.3.3 Lirilumab dose delay/interruption for immune-oncology drug-related AEs, clinically significant in the opinion of the investigator

Lirilumab administration should be delayed for the following drug-related AEs, clinically significant in the opinion of the investigator:

- Any Grade ≥2 non -skin AE, except that

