 - Grade 2 fatigue or laboratory abnormalities do not require delay, however
 - ◆ For a subject with baseline AST, ALT, or total bilirubin within normal limits, delay dosing for drug-related Grade ≥2 values
- Any Grade 3 skin AE, or Grade 3 laboratory abnormality, with the following exceptions:

- Grade 3 lymphopenia or leukopenia does not require dose delay.
- If a subject has Grade 1 baseline AST, ALT, or total bilirubin, delay dosing for drug-related Grade 3 toxicity
 - Any AE, laboratory abnormality, or intercurrent illness, which in the judgment of the investigator, warrants delaying the dose of study medication.
 - Lirilumab dose reductions are not permitted in this study (only dose delays when indicated).

Subjects may resume treatment with study drug when the drug-related AE(s) resolve to Grade ≤ 1 or baseline value, with the following exceptions:

- Subjects may resume treatment in the presence of Grade 2 fatigue
- Subjects who have not experienced a Grade 3 drug-related skin AE may resume treatment in the presence of Grade 2 skin toxicity
- Subjects with baseline Grade 1 AST/ALT or total bilirubin who require dose delays for reasons other than a 2-grade shift in AST/ALT or total bilirubin may resume treatment in the presence of Grade 2 AST/ALT OR total bilirubin
- Subjects with combined Grade 2 AST/ALT AND total bilirubin values meeting discontinuation parameters (Discontinuation Section below) should have treatment permanently discontinued
- Drug-related pulmonary toxicity, diarrhea, or colitis, must have resolved to baseline before treatment is resumed
- Drug-related endocrinopathies adequately controlled with only physiologic hormone replacement may resume treatment

If the criteria to resume treatment are met, the subject should restart treatment at the same dose at the next scheduled timepoint per protocol. The next scheduled time point for 5-azacytidine is the projected day 1 of the next cycle. The next scheduled time point for Lirilumab is the projected day 8 of the next cycle. These will be the next scheduled time points irrespective of the patients current dose level. However, if the treatment is delayed past the next scheduled timepoint per protocol, the next scheduled timepoint will be delayed until dosing resumes. Patients who receive combination therapy in whom continuation of 5-azacytidine is considered to be inadequate, or inappropriate (e.g., because of pancytopenia) can discontinue 5-azacytidine and continue with lirilumab only.

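### For recurrent lirilumab-related events, Table 2 restarts lirilumab at Grade 2 or lower while section 5.3.3 requires Grade 1 or baseline, and the supplied text does not say which prevails

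*Combined protocol and SAP*

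**What the plan says.** Table 2 in section 5.3.2 covers non-hematologic events related to either study drug that the investigator judges clinically significant. Its restart condition for lirilumab depends on how often the event has occurred:

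- 1st or 2nd occurrence, recovering within 14 days: both drugs resume at Grade 1 or lower.
- 1st or 2nd occurrence, lasting 15 to 28 days: 5-azacytidine resumes one level down, with the "prior dose of lirilumab ONLY after recovery to ≤ Grade 2".
- 3rd/4th occurrence, and again at the 5th: "Follow until toxicity ≤ Grade 2. Resume lirilumab at prior dose", with 5-azacytidine reduced by one or two levels.

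The grade column adds an optional extension: "Persistent grade 2: Consider similar dose adjustments if persistent and not responding to optimal management".

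Section 5.3.3 then deals with lirilumab delay for immuno-oncology drug-related events. It says that "Subjects may resume treatment with study drug when the drug-related AE(s) resolve to Grade" 1 or lower, or the baseline value. It accepts Grade 2 fatigue, some liver-test values in patients who started at Grade 1, and endocrinopathies controlled by physiologic hormone replacement. For skin, "Subjects who have not experienced a Grade 3 drug-related skin AE may resume treatment in the presence of Grade 2 skin toxicity". One listed item is stricter than the general rule: "Drug-related pulmonary toxicity, diarrhea, or colitis, must have resolved to baseline before treatment is resumed".

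Section 5.3.4 lists the events for which lirilumab is stopped permanently.

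**The concern.** The same patient on the same day can meet the Table 2 condition for restarting lirilumab and fail the one in 5.3.3. This is a re-dosing rule for a drug whose dose may not be reduced in the phase II part. Short of permanent discontinuation, the hold-and-restart threshold is therefore the main protection against re-exposure after a serious event.

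Table 2 also loosens as events recur. A first event that recovers quickly must reach Grade 1, whereas a third need only reach Grade 2. No reason is given for applying that easing to lirilumab.

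What is at stake is consistent and safe re-dosing, and whether staff have one rule against which compliance can be judged. Section 9.3 lists noncompliance with dose interruption or delay among violations and deviations.

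**Working it through.** No arithmetic applies. The check sets the sections side by side and asks which events receive opposite instructions.

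**Step 1: do the scopes overlap?** Table 2 has no carve-out for lirilumab-related events. Section 5.3.3 covers immuno-oncology drug-related events, and section 5.5 classes lirilumab as an immuno-oncology agent. A clinically significant, lirilumab-related, non-hematologic event therefore falls under both.

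**Step 2: compare the restart conditions for lirilumab.**

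| Situation | Table 2 | Section 5.3.3 | Compatible? |
|---|---|---|---|
| 1st/2nd event, recovery within 14 days | Grade 1 or lower | Grade 1 or lower, or baseline | Yes |
| 1st/2nd event, 15 to 28 days | Not before Grade 2 or lower | Grade 1 or lower, or baseline | Yes: waiting for Grade 1 satisfies both |
| 3rd/4th or 5th event | Resume once Grade 2 or lower | Grade 1 or lower, or baseline | No, outside the 5.3.3 exceptions |

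The second row is a minimum. The third is an instruction to resume.

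**Step 3: remove what 5.3.4 stops.** It ends lirilumab for:

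- Grade 4 drug-related events, apart from certain amylase, lipase and electrolyte abnormalities;
- Grade 3 non-skin events lasting more than 7 days;
- a named list at Grade 3 of any duration (uveitis, pneumonitis, bronchospasm, diarrhea, colitis, neurologic events, hypersensitivity and infusion reactions).

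The 7-day rule does not reach Grade 3 skin events, and it leaves unlisted non-skin events that are at Grade 3 for 7 days or less.

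**Step 4: work through what remains.**

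- *Skin.* A patient has a third Grade 3 lirilumab-related rash, which improves to Grade 2. Section 5.3.4 does not stop treatment. Table 2 says to resume. Section 5.3.3 says to wait, because its Grade 2 skin allowance excludes anyone who has had a Grade 3 drug-related skin event.
- *Unlisted non-skin, non-laboratory.* A third Grade 3 event, other than fatigue or a controlled endocrinopathy, falls to Grade 2 within 7 days and stays there. Table 2 says to resume. Section 5.3.3 says to wait, and itself treats a Grade 2 non-skin event of this kind as a reason to delay.

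In both cases the rules diverge in practice only if the event is still Grade 2 when lirilumab falls due. Section 5.3.3 fixes that date: "The next scheduled time point for Lirilumab is the projected day 8 of the next cycle".

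**Step 5: look for a tie-breaker.** Sections 5.3.1 to 5.3.7 and 5.5 contain no statement of which restart rule prevails. Section 5.3.5 points to algorithms in Appendix G, which is not reproduced in the supplied text.

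**The case against.** The best reply is that ordinary reading settles the matter. Table 2 is a general table for two drugs, and much of it concerns 5-azacytidine dose levels. Section 5.3.3 follows directly, is specific to lirilumab, and gives event-by-event conditions; 5.3.4 completes it. On that view only a cross-reference is missing. Taking 5.3.3 as governing is indeed reasonable. However, Table 2 gives its own explicit lirilumab instruction, and the supplied text nowhere subordinates it.

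A second reply is that clinicians are free to wait. Section 5.3.3 lets the investigator delay for any event thought to warrant it, and 5.3.7.4 permits other interruptions, including of one drug alone, after discussion with the principal investigator and with documentation. This stands: a reader might infer that the protocol forces re-dosing at Grade 2, and it does not. But permission to wait is weaker than the requirement to wait in 5.3.3, and neither clause ranks the two thresholds.

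A third reply relies on attribution: "Investigators should, whenever possible, determine which medication is causing the toxicity and interrupt or dose reduce 5-azacytidine and/or interrupt lirilumab, as applicable". That sentence decides which drug to hold or reduce. It sets no grade for restarting.

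Finally, Appendix G covers skin and other immuno-oncology events and might resolve the point. Section 5.3.5 describes the algorithms as guidance, but they could not be checked, so the finding is limited to the supplied text.

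**Conclusion.** The conflict is real and narrow. It lies in the 3rd/4th and 5th occurrence rows of Table 2. Its clear cases are recurrent Grade 3 lirilumab-related skin events that have improved only to Grade 2, and the unlisted Grade 3 non-skin, non-laboratory events described above.

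Several wider readings are tempting but not supported:

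- *First and second events.* The 15-to-28-day branch also mentions Grade 2, but as a floor that can be met together with 5.3.3.
- *Laboratory abnormalities.* These are a weaker case. Section 5.3.3 does not require delay for most Grade 2 laboratory values, although its general restart sentence asks for Grade 1 or baseline. That ambiguity sits inside 5.3.3.
- *Persistent Grade 2 events.* Table 2 only asks that similar adjustments be considered, so any conflict depends on the investigator choosing to apply it.
- *A rate or a count.* Few patients should be affected, because the problem needs a third or later event, no stop under 5.3.4, and Grade 2 still present on the dosing day. The number cannot be derived: the background safety data give no rate of recurrence under this combination, and Table 2 does not say whether occurrences are counted per event type or across all events.
- *Effect on the analysis.* There is none on the overall response rate or the stopping boundaries. The toxicity boundary in section 11.2 counts patients with a drug-related Grade 3/4 event, and the patients in the clear cases have already had one whichever restart rule is used.

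The conclusion assumes that lirilumab-related events fall within 5.3.3, as section 5.5 indicates, and that Appendix G does not already set a precedence. It merits a minor safety-rule correction.

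**What to change.** Amend Table 2 to state that, for lirilumab-related events, resumption of lirilumab follows 5.3.3 (Grade 1 or lower or baseline, with its listed exceptions and its stricter rule for pulmonary toxicity, diarrhea and colitis) and permanent discontinuation follows 5.3.4. Table 2's Grade 2 threshold and dose-level reductions would then govern 5-azacytidine only. Check the wording against Appendix G before it is issued.

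The cost is amendment text and a memo to study staff; sample size, endpoints and boundaries do not change. The clinical downside is an occasional deferred lirilumab dose, or discontinuation if the delay exceeds 8 weeks and no exception applies under 5.3.4 or the clinical-benefit provision in 5.2.2.2.

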5.3.4 Lirilumab Discontinuation Criteria

Treatment should be permanently discontinued for the following:

- Any Grade 2 drug-related uveitis or eye pain or blurred vision that does not respond to topical therapy and does not improve to Grade 1 severity within the re-treatment period OR lasting > 7 days with systemic treatment
- Any Grade 3 non-skin, drug-related adverse event lasting > 7 days, with the following exceptions for drug-related laboratory abnormalities, uveitis,

pneumonitis, bronchospasm, diarrhea, colitis, neurologic adverse event, hypersensitivity reactions, and infusion reactions:

- Grade 3 drug-related uveitis, pneumonitis, bronchospasm, diarrhea, colitis, neurologic adverse event, hypersensitivity reaction, or infusion reaction of any duration requires discontinuation
- Grade 3 drug-related laboratory abnormalities do not require treatment discontinuation except those noted below:
- Any drug-related liver function test (LFT) abnormality that meets the following criteria require discontinuation: AST or ALT > 8 x ULN
- Any Grade 4 drug-related adverse event or laboratory abnormality, except for the following events which do not require discontinuation:
 - Isolated Grade 4 amylase or lipase abnormalities that are not associated with symptoms or clinical manifestations of pancreatitis and decrease to < Grade 4 within 1 week of onset.
 - Isolated Grade 4 electrolyte imbalances/abnormalities that are not associated with clinical sequelae and are corrected with supplementation/appropriate management within 72 hours of their onset
- Any dosing interruption lasting > 8 weeks with the following exceptions:
 - Dosing interruptions to allow for prolonged steroid tapers to manage drug-related adverse events are allowed. Prior to re-initiating treatment in a subject with a dosing interruption lasting > 8 weeks the Investigator must be consulted. Tumor/Leukemia assessments should continue as per protocol even if dosing is interrupted.
 - Dosing interruptions > 8 weeks that occur for non-drug-related reasons may be allowed if approved by the Investigator. Prior to re-initiating treatment in a subject with a dosing interruption lasting > 8 weeks the Investigator must be consulted. Tumor/Leukemia assessments should continue as per protocol even if dosing is interrupted.

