5.3.5 Detailed management algorithms for immune-oncology drug-related adverse events (including gastrointestinal, renal, pulmonary, hepatic, endocrine, skin and neurological) are provided in Appendix G. These general guidelines constitute guidance to the Investigator and may be supplemented by discussions with the Medical Monitor representing the Sponsor in specific cases.

5.3.6 Intra-patient dose re-escalation of 5-azacytidine for patients who have had dose-reductions due to hematological or non-hematological toxicity:

Once the MTD has been established in the lead-in, the lirilumab dose will not be reduced or escalated during the phase II. Intra-patient dose re-escalation of 5-azacytidine (in accordance with the dosing schema in table 1) will be permitted provided:

- Patient has completed ≥ 1 cycle at their current dose level
- Patient has not experienced any grade 3 or higher non-hematologic drug-related toxicity, and
- Patient has not experienced drug-related hematologic DLT, and
- At least 6 patients have been treated at the next higher dose level and followed for at least 28 days without experiencing DLT.
- The dose may be escalated by one dose level per cycle (per table 1) provided such dose level does not exceed the established MTD or dose level 0, whichever is lower. Dose level 0 is the maximum dose allowed on this study. No dose escalation beyond dose level 0 will be permitted.

5.3.7 Modifications of dose schedules other than the above will be allowed within the following guidelines:

5.3.7.1 Further dose reductions can be made to keep clinically significant toxicities grade ≤ 2 .

5.3.7.2 Dose adjustments by more than 1 dose level at a time (e.g., from 5-azacytidine 75 mg/m² to 25 mg/m²) can be considered when judged in the best interest of the patient (e.g. severe myelosuppression) when toxicity has resolved. The reason for this reduction will be discussed with the PI or Co-PI and documented in the medical record.

5.3.7.3 A patient who has had a dose reduction because of any of the reasons mentioned above may have their dose escalated provided the patient has remained free of toxicity requiring dose adjustments as defined above for at least 1 month. Escalation will be made by 1 dose-level increment only, and not more frequent than every month.

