9.1.3 Criteria for Protocol-Defined Required Discontinuation of Treatment

The protocol requires discontinuation of study treatment for the following reasons:

1. Patient requests discontinuation.
2. Unacceptable toxicity that in the opinion of the investigator makes it unsafe to continue therapy.
3. Clinically significant progressive disease.

4. Investigator discretion.

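### Section 5.3.3 orders a permanent stop for combined Grade 2 AST/ALT and bilirubin values by reference to parameters that section 5.3.4 does not contain, so the stop has no operative liver-value trigger

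*Combined protocol and SAP*

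**What the plan says.** Section 5.3.3 covers delays of lirilumab for drug-related events and the conditions for restarting. The general condition is recovery to Grade 1 or lower, or to baseline, with listed exceptions. Two of these concern the liver:

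- Patients with Grade 1 baseline values, delayed for a reason other than a two-grade rise, "may resume treatment in the presence of Grade 2 AST/ALT OR total bilirubin".
- For the combined case: "Subjects with combined Grade 2 AST/ALT AND total bilirubin values meeting discontinuation parameters (Discontinuation Section below) should have treatment permanently discontinued".

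The discontinuation section that follows is 5.3.4. It says "Grade 3 drug-related laboratory abnormalities do not require treatment discontinuation except those noted below", and the liver line under that statement is "Any drug-related liver function test (LFT) abnormality that meets the following criteria require discontinuation: AST or ALT > 8 x ULN". It also stops treatment for "Any Grade 4 drug-related adverse event or laboratory abnormality, except for the following events which do not require discontinuation"; those exceptions concern amylase or lipase and electrolytes. Bilirubin is not named anywhere in 5.3.4.

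**The concern.** Section 5.3.3 treats one raised liver measure (OR) differently from both raised together (AND). The first can allow a restart; the second is meant to end treatment. The combined case was therefore singled out on purpose, but the rule for it depends on parameters held in another section, and that section has none for the combination.

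Three things are at stake:

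- **Patient handling.** The same combined abnormality could lead to a permanent stop or to re-treatment, depending on how the two sections are read together.
- **Compliance.** Section 9.3 makes departure from discontinuation criteria a class of violation or deviation. For this case, compliance cannot be judged.
- **Data.** Treatment exposure and the recorded reason for ending treatment would vary with the reading adopted.

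**Working it through.** No arithmetic applies. The check sets the condition in 5.3.3 (Grade 2 AST/ALT together with Grade 2 total bilirubin) against each criterion in 5.3.4, then looks for a parameter elsewhere.

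**Step 1. Criteria in 5.3.4**

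| Criterion in 5.3.4 | Met by combined Grade 2 liver values? |
|---|---|
| Grade 2 eye events | No, not a liver finding |
| Grade 3 non-skin events beyond 7 days | No, values are Grade 2 |
| Named Grade 3 events of any duration | No, wrong grade and no liver event named |
| AST or ALT > 8 x ULN | No, see step 2 |
| Grade 4 events or laboratory values | No, values are Grade 2 |
| Interruption > 8 weeks | Not by the values; only if a delay lasts that long |

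Five of the six are not met, and the sixth depends on elapsed time.

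**Step 2. Why the 8 x ULN line does not supply the trigger.** First, it appears as an exception to the statement that Grade 3 laboratory findings do not require a stop, so on the protocol's own ordering it lies above Grade 2. Second, it ends treatment on AST or ALT alone. If it were the intended parameter, the bilirubin half of the instruction in 5.3.3 would do no work.

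**Step 3. Other text**

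- *Delay rules, 5.3.3.* "For a subject with baseline AST, ALT, or total bilirubin within normal limits, delay dosing for drug-related Grade ≥2 values". This is a delay, not a permanent stop. Patients with Grade 1 baseline values are delayed at Grade 3, so combined Grade 2 values bring them no mandatory delay, only one at the investigator's judgment.
- *Table 2, 5.3.2.* Grade 1 or 2 events lead to no dose reduction, with similar adjustments to be considered for persistent Grade 2. Grade 3 or 4 events are held, with resumption after recovery. There is no permanent liver stop.
- *DLT definition, 5.2.1.3.* It does not reach combined Grade 2 values.
- *Sections 5.4 and 9.1.3.* General grounds only, such as "Unacceptable toxicity that in the opinion of the investigator makes it unsafe to continue therapy", and investigator discretion.
- *Section 5.3.5.* "Detailed management algorithms for immune-oncology drug-related adverse events (including gastrointestinal, renal, pulmonary, hepatic, endocrine, skin and neurological) are provided in Appendix G". The section calls these guidance, and 5.3.3 does not refer to them.

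**Step 4. Resulting readings for a patient with combined Grade 2 values**

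- *Literal:* the stop applies only if a 5.3.4 parameter is met; none is, so the patient may restart under the general recovery rule.
- *By intent:* the combination is itself the ground for stopping, so treatment ends permanently.

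Both can be defended from the text, and they lead to opposite actions.

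**The case against.** The strongest reply is that the missing parameter leaves little unprotected. Any Grade 4 drug-related bilirubin or transaminase value ends treatment. So does a delay beyond 8 weeks, with exceptions. Section 9.1.3 requires a stop for unacceptable toxicity and at investigator discretion. Baseline-normal patients are delayed from Grade 2 and in general restart only at Grade 1 or lower or at baseline, while Grade 3 or 4 toxicity is held under Table 2. Re-treatment would therefore mostly follow recovery. All of this stands, and it limits the consequence.

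A second reply is that the instruction could bar restart for a patient now at combined Grade 2 who earlier met a 5.3.4 criterion. That reading is possible but not the natural one. It would also make the instruction redundant, since 5.3.4 would already have ended treatment.

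A third is that Appendix G or the Investigator Brochure may hold a combined threshold. Their content is not in the text reviewed, so this cannot be excluded. But 5.3.3 directs the reader to the discontinuation section, not to either of them.

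Three stronger claims are tempting and are not supported:

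- A reader might infer that a Grade 3 bilirubin with transaminases at or below 8 x ULN escapes every discontinuation rule. It does not, because the time-based and judgment-based stops still apply, as does the Grade 4 rule if it worsens.
- A reader might expect sites to diverge. Section 11.0 describes a single-center study and 7.2.9 has all lirilumab given there, so only differences between investigators at that center are in question.
- A reader might try to express the gap between Grade 2 and the 8 x ULN line in multiples of ULN. That needs CTCAE cut-offs, and Appendix C is not reproduced.

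**Conclusion.** The point holds in a limited form. A stated patient-safety stop refers to parameters that are absent from the section it cites, so combined Grade 2 AST/ALT and bilirubin values trigger no liver-value criterion. This is an internal inconsistency in one instruction; liver-related stopping is not absent from the protocol.

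The number of patients affected cannot be estimated from the documents. No effect on the response-rate estimate, the sample size or the monitoring boundaries is shown; Table 4 counts Grade 3/4 drug-related toxicities, so a combined Grade 2 event would not enter it.

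The conclusion assumes that 5.3.4 is complete as supplied. Its liver line announces criteria in the plural and then gives one, which is consistent with an omitted entry but does not prove one. It also relies on the grade ordering within 5.3.4, not on any outside grading table.

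**What to change.** The sponsor should reconcile 5.3.3 with 5.3.4 in one of two ways:

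- State in 5.3.4 the combined AST/ALT-and-bilirubin parameter that 5.3.3 refers to. This should cover patients entering with raised values: 4.1.7 allows AST or ALT up to 5.0 x ULN when attributed to leukemia, and bilirubin up to 3 x ULN when attributed to leukemia or Gilbert's syndrome. The baseline-specific liver rules in 5.3.3 address only normal and Grade 1 baselines.
- If no such parameter is intended, remove the cross-reference and say which rule governs the combined case.

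The choice of rule and of any value belongs to the sponsor; none is suggested here. If Appendix G already holds the intended parameter, 5.3.3 should cite it and say whether it is binding.

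The cost is one added bullet or one deleted clause, with a sentence on baseline values. No new tests are needed: 7.2.3 already schedules ALT and total bilirubin weekly for the first 3 cycles and every 2-4 weeks thereafter.
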